### **Statistical Analysis:**

For the analysis of the elastic moduli, tensile strength, and percentage of elongation properties of the NDGP, a two-tailed Student's t test was used.  $\alpha$  was set at 0.05, and P values <0.05 were considered statistically significant. All tests were performed in triplicate, and statistical analyses were conducted using MATLAB R2014a (MathWorks Inc.).

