**NCT02698163**

**Study Protocol in Submitted UCLA IRB#15-002015 (March 4th, 2020)**

## **Summary:**

Non-surgical root canal therapy (RCT) represents a standard of treatment that addresses infected pulp tissue in teeth and protects against future infection while preserving the tooth for the patient. RCT involves removing dental pulp comprising blood vessels and nerve tissue, followed by the placement of filler material to occupy the naturally occurring space where the pulp was removed. Currently, standard of care treatment for RCT utilizes gutta-percha (GP) as the root canal filling material. Tooth extraction is necessary if the RCT fails or if the tooth fractures. The need for extraction after failed RCT might be reduced by increasing the strength of the canal filling material closer to that of dentin. Nanodiamonds (NDs) may offer unique advantages due to their favorable properties, particularly for dental applications. In this prospective pilot study, we will utilize gutta-percha modified with nanodiamonds 5 wt % (NDGP) as the root canal filling material. Our research group has previously demonstrated NDGP's improvement in tensile strength compared to those of gutta-percha. We hypothesize that NDGP will not have a negative effect on clinical outcome for the patient compared to the GP. Additional potential positive benefits include decrease in void space and better clinician handling of NDGP during the canal filling procedure. NDGP with its increased mechanical properties, potential decrease in void space between the NDGP and the tooth's root, and the ease of handling by clinician of NDGP during vertical obturation procedure may result in a decrease in the pain experienced by the NDGP patients compared to those experienced by the control (GP) patients. Patients will be recruited and randomized into two RCT filler material patient groups for this study: 15 patients for the control, 15 patients with NDGP. For all the patients into the control arm of the study, the root canals will be filled with GP at the bottom third up to and including the top third, using a standard procedure involving vertical condensation obturation. For all the patients into the treatment arm of the study, the root canals will be filled with GP at the bottom third, NDGP in the middle third, and again with GP at the top third, using the vertical condensation obturation technique. The tooth will be restored with a crown for posterior teeth, or a composite filling for anterior teeth. There will ideally be a total of four visits: consultation appointment (~1 hour), RCT appointment (~2-3 hours), 6 month follow-up appointment (~1 hour), and 1 year follow-up appointment (~1 hour). Additional follow-up appointments (~1 hour) prior to the 6 month and 1 year follow-up appointments may be required in the event of infection or persistent pain of the root canal. Patient data will be categorized by age, weight, gender, and use of other drugs which may alter the pain assessment and pilot study success indicators. This study investigates a new type of filler, gutta-percha modified by the addition nanodiamond material (NDGP), which may be stronger and prevent complications of RCT such as tooth fracture to improve treatment outcomes.

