
## **Study Protocol:**

[name] will recruit the patient for this study after the patient's referral to the UCLA endodontics department for root canal therapy. Informed consent will be obtained by [name] from all the patients that will be able to be taken home for patients to consider being part of this pilot study. We will stress to the patient that there will be an intended benefit and that we will be providing an incentive for joining this study (parking vouchers). The sample population will be screened and collected [name], M.S.,

Ph.D., D.D.S. All of the patients must be over 18 years of age when the treatment commences. Teeth will be excluded from this study if they had preoperative periodontal disease, prior non-surgical and surgical endodontic treatment, or if the apex/apices under investigation is/are not discernible in any of the periapical radiographs. The teeth that will be excluded from the analysis of the 'periapical status following treatment' are if: (1) they were not followed-up for at least 6 months, (2) if they were extracted for reasons not related to endodontic problems (for e.g. periodontal disease), (3) information on the periapical status during the time of extraction was not available.

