5.25% Sodium hypochlorite (NaOCl) solution will be the standard root canal irrigant. Root canal preparation cream (Premier, Plymouth Meeting, PA, USA) will be used as an intracanal lubricant if needed. Calcium hydroxide (Ca(OH)2) will be the standard interappointment medicament for teeth with acute pulpitis if removal of pulp tissues at the first visit was incomplete.

Patients will be randomized according to a predetermined order created by [name] and [name] via Matlab. 30 patients will be assigned a number 1-30 according to the order of recruitment for this study 1 being assigned to the first patient recruited and 30 to the last patient recruited for this study. The randperm(30,15) function will be used to create a list of 15 numbers from the 30 (recruitment order number). This list of 15 numbers (recruitment order numbers) will be the Nanodiamond gutta percha (NDGP) group to receive the NDGP filler material. The remaining 15 numbers will be given the standard of care gutta-percha filler material. This list will be arranged accordingly for the clinicians' reference.

For all the patients into the control arm of the study, the root canals will be filled with gutta percha at the apical third up to and including the coronal third, using the vertical condensation obturation technique, also known as the modified Schilder's warm vertical compaction technique (Van Zyl et al. 2005). The root canal sealer used will be zinc oxide-eugenol (Kerr Corporation, Orange, CA, USA). After the root canal treatment is done, the patient will be treated by [name], a general dentist for the restorative aspect of the procedure. Depending on how much tooth structure is left, he will decide which kind of build-up material to use and if a post is needed. The tooth will be restored with a crown for posterior teeth, or a composite filling for anterior teeth.

For all the patients into the treatment arm of the study, the root canals will be filled with gutta percha at the apical third, Nanodiamond gutta percha (NDGP) in the middle third, and again with gutta percha at the coronal third, using the vertical condensation obturation technique, also known as the modified Schilder's warm vertical compaction technique (Van Zyl et al. 2005). The root canal sealer used will be zinc

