oxide-eugenol (Kerr Corporation, Orange, CA, USA). After the root canal treatment is done, the patient will be treated by [name], a general dentist for the restorative aspect of the procedure. Depending on how much tooth structure is left, he will decide which kind of build-up material to use and if a post is needed. The tooth will be restored with a crown for posterior teeth, or a composite filling for anterior teeth.

The goal is to follow-up all treated teeth 6 months and 1 year post-RCT. Appointment letters will be mailed to the patients 1 month prior to the follow-up dates. Patients, who failed to attend for recall, will be contacted with a personal courtesy call by the study team member (dentist on study team) and a more detailed explanation letter will be mailed to encourage them to attend follow-up appointments. If patients continue to not attend for recall, then the reasons provided by each patient (if provided) will be recorded. Recall appointments can be made as necessary other than the 6-month and 1-year follow-up appointments. Recall appointments will have their own specific form detailing the patient's reason and required procedure. Possible complications will be communicated to the patient prior to the study and will be dealt with on a case by case basis.

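### The hypothesis that NDGP does no harm to clinical outcome has no patient-outcome analysis behind it: the only statistical method is a t test on bench properties, with no between-arm comparison, interval, margin or primary time point

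*Combined protocol and SAP*

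**What the plan says.** The Summary states the comparative hypothesis: "We hypothesize that NDGP will not have a negative effect on clinical outcome for the patient compared to the GP". It calls the study a prospective pilot and gives the groups as "15 patients for the control, 15 patients with NDGP". The randomisation paragraph of the Study Protocol section allocates by patient: "30 patients will be assigned a number 1-30 according to the order of recruitment".

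The treatment-success paragraphs of the same section name two outcomes, absence of apical periodontitis (clinical and radiographic) and tooth survival. They define success strictly as no pain, no signs of inflammation or swelling, and complete radiographic healing. A looser version that admits incomplete healing follows as a possible consideration. On timing, the section says: "The goal is to follow-up all treated teeth 6 months and 1 year post-RCT". Neither visit is named as primary.

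The recruitment paragraph removes teeth from the analysis of periapical status after treatment in three cases:
- "they were not followed-up for at least 6 months"
- "if they were extracted for reasons not related to endodontic problems"
- "information on the periapical status during the time of extraction was not available"

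The later paragraph on complications counts extraction for endodontic problems as a failed outcome. It then excludes from analysis any extraction with no postoperative periapical information, without saying which outcome is meant.

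The Statistical Analysis section is a single paragraph. It opens "For the analysis of the elastic moduli, tensile strength, and percentage of elongation properties of the NDGP", applies a two-tailed Student's t test at α = 0.05, and reports in the past tense that tests were run in triplicate.

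**The concern.** The one method given cannot be applied to the trial's question. Triplicate testing of moduli, strength and elongation describes laboratory specimens, whereas the two clinical outcomes are yes/no results in randomised patients. So the hypothesis has no effect measure, no interval, and no statement of what result would support it.

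Two things are at stake. First, with no margin and 15 per arm, similar success counts or a non-significant difference could be reported as showing no harm, although the data would still be compatible with a substantial loss. Second, the time point and the handling of teeth removed after randomisation are left to be settled after results are seen, and in a comparison this small a few teeth matter. The extraction exclusion is a particular worry because an extraction is itself a tooth-survival event.

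**Working it through.** **Step 1: is there a patient-outcome analysis anywhere?** Setting the sections side by side:

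| Item | Where stated | Content |
|---|---|---|
| Comparative hypothesis | Summary | NDGP not worse than GP on clinical outcome |
| Outcomes | Study Protocol, treatment success | Periapical (strict definition first); tooth survival |
| Time point | Study Protocol, follow-up | 6 months and 1 year; none primary |
| Between-arm method, interval, margin | – | None for any patient outcome |
| Statistical method | Statistical Analysis | t test on bench properties |

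The sample size of 30 comes with no power, effect size or derivation, so there is no stated figure to reproduce.

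**Step 2: what precision do 15 per arm give?** Inputs:
- n = 15 per arm (Summary).
- A success rate of 86%, a background remark about primary root canal treatment in the complications paragraph, given without a definition or time point.
- Assumptions of mine: one evaluable tooth per patient, all 15 per arm analysed, and a two-sided 95% level (z = 1.96).

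Wilson limits for x/n, with p = x/n:

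(p + z²/2n ± z·√[p(1−p)/n + z²/4n²]) / (1 + z²/n)

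Newcombe lower limit for p₁ − p₂ (NDGP minus GP):

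(p₁ − p₂) − √[(p₁ − l₁)² + (u₂ − p₂)²]

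The upper limit is the mirror image. With equal results in the two arms:

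| Each arm | Wilson limits | Half-width |
|---|---|---|
| 15/15 | 0.796 to 1.000 | √(0.204² + 0²) = 20.4 points |
| 14/15 | 0.702 to 0.988 | √(0.231² + 0.055²) = 23.8 points |
| 13/15 | 0.621 to 0.963 | √(0.245² + 0.096²) = 26.4 points |
| 12/15 | 0.548 to 0.930 | √(0.252² + 0.130²) = 28.3 points |

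If exclusions left 12 per arm (an assumption), equal results give ±24.2 points at 12/12 and ±30.6 at 10/12.

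Averaging the half-width over two independent Binomial(15, 0.86) arms gives 26.1 points. The average is 28.7 at a true rate of 76% and 24.8 at 90%. As a rough check, the Wald formula gives 1.96·√(2 × 0.86 × 0.14 / 15) = 0.248, or about 25 points.

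**Step 3: can exclusions matter?** This is an illustration with invented counts only. Suppose 3 NDGP teeth and 1 GP tooth are lost to follow-up.
- Excluding them: 11/12 v 12/14 = 0.917 − 0.857 = +6.0 points (95% −23.0 to +32.5).
- Counting all four as failures: 11/15 v 12/15 = 0.733 − 0.800 = −6.7 points (−35.1 to +23.0).

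The sign can change. This shows what is arithmetically possible, not what will happen.

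**Step 4: the two exclusion rules.** The recruitment paragraph ties its list to periapical status. The complications paragraph repeats the third item in substance but names no outcome. Read literally, it would also drop those extractions from tooth survival.

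**The case against.** The best defence is that this is a pilot with defined outcomes, that wide intervals are normal in a pilot, and that no formal no-harm test is promised. The complications paragraph even warns against attributing failures to the material. Much of this stands. Lack of power is not an error here, and the outcomes are not missing. What remains is a comparative hypothesis with no comparison specified.

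A reader might infer more than the documents support on four counts:

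- **That the definition of success is wide open.** It is not. The strict definition comes first and the looser one is only a possible consideration. The looser one also needs a lesion that can shrink, and patients with periapical radiolucency (minimum size still to be set) are excluded. The real gap is the time point.
- **That the unit of analysis might be the root.** The per-root classification describes preoperative status only, and the text generally speaks of one tooth per patient. One tooth per patient is never stated outright, so a clarifying phrase is enough.
- **That extractions will be dropped from tooth survival.** The wording permits this, but the complications sentence probably just repeats the periapical-only rule.
- **That the exclusions will reverse the result.** The reversal above rests on invented counts.

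The choices of Newcombe and of 1 year are preferences. Another small-sample interval or time point would do if fixed in advance.

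**Conclusion.** The concern holds: the plan as written yields no between-arm result for either named clinical outcome, and so none for its own hypothesis. That finding rests on the text alone and needs no numerical assumption.

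A no-harm conclusion from 15 per arm would also not be supportable. Even if every tooth in both arms succeeded, the interval would reach a 20.4-point deficit, and the documents state no margin against which to judge that. The limit is not a fixed figure. It widens to 26.4 points at 13/15 and 28.3 at 12/15 in each arm, averages about 26 at 86% true success, and grows with exclusions. These sizes assume one tooth per patient, 15 analysed per arm and two-sided 95% Newcombe intervals.

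This should be corrected before outcomes are examined, because a missing analysis cannot credibly be chosen afterwards.

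**What to change.** 1. Label the t test in the Statistical Analysis section as bench background.
2. Restate the hypothesis as a pilot estimation aim, with no no-harm conclusion to be drawn.
3. Before outcomes are examined, fix one time point (for example 1 year) for the strict success definition. Report the NDGP minus GP difference in strict success and in tooth survival, by randomised arm, with one study tooth per patient and a two-sided 95% small-sample interval such as Newcombe. Make the looser definition and the other time point secondary.
4. State that both exclusion rules apply to periapical status only, so that every extraction counts in tooth survival. Show non-endodontic extractions separately, and keep the existing rule that extraction for endodontic problems is a failure.
5. State how teeth seen at 6 months but not at 1 year enter the main analysis. For analysis purposes only, count a tooth that needed secondary root canal treatment because the primary treatment failed as not a strict success.
6. Report losses and exclusions by arm with reasons. Add a sensitivity analysis on all randomised and treated patients that counts as failures the teeth lost to follow-up or extracted without periapical information.
7. State the expected precision: about ±26 points near 86% success, and wider with exclusions.

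The cost is about a paragraph of statistical text, one table of losses and exclusions, a little more analysis, and a less ambitious stated aim. Counting lost teeth as failures lowers the success rates, which is why it is a sensitivity analysis and not the main result. Sample size, visits and treatment are unchanged.
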